3.2 Subject Disposition

Subject disposition will be summarized for the ITT population. The following data will be presented:

- The number and percentage of subjects who completed or discontinued prematurely from the study by treatment group. The number and percentage of subjects who discontinued for each reason will be presented for each treatment group (Table 3.2.1). The number and percentage of subjects who completed or discontinued prematurely in each treatment group will also be displayed graphically (Figure 3.2.1).
- A listing of subjects that discontinued prematurely from the study. The listing will include information about treatment, study center, subject number, age, race, number of sessions on treatment, and reason for discontinuation (Table 3.2.2), and the percentages of the completion and discontinuation by site will be presented (Table 3.2.3).

The number of subjects that were enrolled at each study center and the number and percentage of subjects that completed or discontinued at each study center will be summarized for each treatment group and for all subjects.

The end of trial CRF will be used to determine who discontinued prematurely from the study.

3.3 Analysis Populations

Intent-to-Treat (ITT) – This population includes all subjects who were randomized to the study. Subjects will be assigned for analysis according to the group to which they were randomized.

Completers – This population includes all ITT subjects who patients who were treated according to the protocol and had fewer than 4 TMS sessions not completed during acute treatment phase (George et al 2010).

Fully Compliant – This population includes all ITT subjects who had fewer than 2 sessions not completed and had no other treatment related protocol violations during acute treatment phase (George et al 2010).

Safety – This population includes all subjects who received at least one session of the rTMS treatment. The number of subjects in each population will be summarized for each treatment group and for all subjects (Table 3.3.1).

3.4 Study Treatment Session and Compliance

Study rTMS treatment session and compliance will be summarized by treatment group and overall for the ITT population.

3.4.1 Study Treatment Session

The following information will be presented for each treatment group and overall (Table 3.4.1):

- Summary statistics (number of subjects with data, mean, median, SD, minimum, and maximum) for the number of sessions of rTMS treatment.
- The number and percentages of subjects in each of the following categories of the acute treatment: 0-5, 6-10, 11-15, 16-19, ≥ 20 sessions.

3.4.2 Study Treatment Compliance

The following information will be presented for each treatment group and overall for compliance:

- Summary of protocol noncompliance (Table 3.4.2)
- Summary statistics (number of subjects, mean, median, SD, minimum, and maximum) for treatment compliance (Table 3.4.3)
- The number and percentage of subjects in each of the following categories of compliance: $\leq 70\%$, $>70\%$ - 80% , $>80\%$ - 90% , and $>90\%$ (Table 3.4.3)

3.5 Subject Demographics and Pre-Treatment Characteristics

Subject demographics and pre-treatment characteristics will be summarized for the Intent-to-Treat population. The demographics and pre-treatment characteristics will be summarized for each treatment group and for all subjects.

3.5.1 Demographics

The summary of demographics at baseline will include:

- The number and percentage of subjects with each category of race, gender, ethnicity, marital status, education, military history, location of military service, branch of service, work history, type of job, type of payment, income, income past four weeks, and pregnancy test results.

- The sample size, mean, median, SD, minimum, and maximum values for age, weight, and height. Age will be calculated as follows:
 - Age = Largest Integer \leq [(Screening Visit Date – Date of Birth +1)/365.25]
 - Weight at screening from physical examination CRF will be used for the summary
 - BMI = (Weight/Height²)*100². The unit of weight will be kilogram and the unit of height will be centimeter.

Summary of the demographics characteristics of the subject population will be presented for ITT, completer, and full compliance populations (Tables 3.5.1a-c), as well as other chosen subgroups which may be presented if the populations are very different from ITT. Significance tests of the balances between the two treatment groups will be performed and p-values will be presented.

3.5.2 Outcome Measures at Baseline

Baseline comparability among the treatment groups will be evaluated with respect to baseline values of outcome measures besides the demographic variables. The sample size, mean, median, SD, minimum, and maximum values for the psychological and cognitive functional measures will be summarized for each treatment group and all subjects (Tables 3.5.2a-c). Significance tests of the balances between the two treatment groups will be performed and p-values will be presented.

3.5.3 Medical History

The number and percentage of subjects reporting a medical history will be summarized by the following medical conditions: Allergies, HEENT disorder, Cardiovascular disorder, Renal disorder, Hepatic disorder, Pulmonary disorder, Gastrointestinal disorder, Musculoskeletal disorder, Neurological disorder, Psychiatric disorder, Dermatologic disorder, Metabolic disorder, Hematologic disorder, Endocrine disorder, Genitourinary disorder, Reproductive system disorder, and Traumatic brain (Tables 3.5.3a-c).

3.5.4 Pre-randomization Signs and Symptoms (Adverse Events)

Pre-randomization signs and symptoms will be coded using MedDRA updated version. Any adverse event that has a start date prior to the date of the randomization

will be summarized as pre-randomization adverse events. The number and percentage of subjects reporting each pre-randomization adverse events will be summarized by body system. The number and percentage of subjects reporting any pre-randomization adverse events will also be reported (Tables 3.5.4a-c). If a subject reports the same pre-randomization adverse event more than once, then that subject is only counted once for the summary of that pre-randomization adverse event, using the most severe intensity.

3.6 Prior and Concomitant Medications

Concomitant medications are recorded every week in acute and taper treatment phases, and every other four weeks in the follow-up phase. Each summary below will be done for each treatment group and for all subjects:

- Prior medications – Prior medications are considered to be any medication that was stopped prior to the date of the randomization
- Concomitant medications – Concomitant medications are considered to be any medication that was taken on or after the date of the first dose of study drug
- All medications recorded on the CRF are coded to the therapeutic drug classes and generic drug names using the World Health Organization (WHO) drug classifications
- The current version of the World Health Organization (WHO) drug dictionary are used for the coding of medications

Each summary will give the number and percentage of subjects who took medications that were coded to each generic drug name and therapeutic drug class, as well as the number and percentage of subjects that took any medication.

Summaries for prior medications will be done for ITT medications (Table 3.6.1), while summaries for concomitant medication will be done for ITT (Table 3.6.2a), completer (Table 3.6.2b), and fully compliant (Table 3.6.2c), populations.

3.7 Efficacy Analyses

The primary endpoint analysis will be done for the ITT population. All secondary and other efficacy analyses will be done for the ITT, completer, and fully compliant populations, unless otherwise specified. Potential difficulties of convergence of model fit, which arise in efficacy analyses that include covariates, will be handled using the method described in Section 3.7.1.

At the completion of the follow-up phase for all subjects in the clinical trial, the efficacy endpoints analyses will be performed. The primary efficacy analysis is based on the measurements of Hamilton Rating Scale for Depression (HRSD). The other key efficacy analyses will include:

- Depression measured by Montgomery-Asberg Depression Rating Scales (MADRS)
- Depression measured by Beck Depression Inventory (BDI)
- Suicide Ideation measured by Beck Scale for Suicide Ideation (BSS)
- Quality of Life measured by the VR-36
- Cognitive Function as measured by a neuropsychological battery

All endpoints will be summarized for all visits once the study is complete.

3.7.1 Primary Efficacy Analysis

3.7.1.1 Primary Endpoint Analysis

The primary endpoint is the proportion of subjects in each treatment group who achieve “remission” from depression at the end of the acute treatment phase (after a maximum of 30 sessions). “remission” is assessed by a HRSD score ≤ 10 at the end of the acute treatment session (after a maximum of 30 sessions). For patients who dropout before completing the acute treatment phase will be considered treatment failures for the primary analysis on remission rates. The primary null hypothesis is that there is no difference between the treatment and sham groups in the proportion of subjects who are remitted during the acute treatment phase. The primary variable is defined in Section 2.4.1.

Logistic regression will be used for the primary endpoint ($Y = 1$ if remitted,

otherwise $Y = 0$) analysis on the ITT population with treatment group as the testing factor (x). The following covariates will be included in the model: PTSD diagnosis (yes/no as assessed by SCID, z_1), History of substance abuse (yes/no as assessed by SCID, z_2), and Site (9 participating sites, z_3). Given the remission probability $p = \Pr(Y = 1 | x, z_1, z_2, z_3)$ the basic model is defined as follows:

$$\log it(p) = \ln\left(\frac{p}{1-p}\right) = \beta_0 + \beta_1 x + \beta_2 z_1 + \beta_3 z_2 + \beta_4 z_3$$

In the event that the logistic regression does not converge when all covariates are included, the model will be refit by dropping the covariates from the model one at a time in the following order until convergence is obtained.

- a. History of substance abuse
- b. PTSD diagnosis
- c. Site

The number and percentage of subjects in remission at the end of the acute treatment will be summarized and compared using Pearson χ^2 test (Table 3.7.1a). Odds ratio and 95% confidence interval (CI) will be presented using SAS PROC GENMOD. If the coefficient for treatment effect is significant (i.e., the confidence interval for the odds ratio does not include 1), then the null hypothesis will be rejected (McCullagh and Nelder, 1989). The significant level for each covariate coefficient in the model will best determined by Wald test (Table 3.7.1b).

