2.6 Sample Size Consideration

The primary hypothesis of the study is that in VA patients with TRMD, rTMS will result in a greater remission rate at the end of acute treatment than sham rTMS. The primary outcome measure in this study is success or failure to achieve remission from depression as defined by a score on the Hamilton Rating Scale for Depression (HRSD24) of 10 or less. The primary analysis will be done as an "intent-to-treat" analysis, i.e. patients will be analyzed in the groups to which they were randomized and drop-outs will be considered treatment failures. The primary hypothesis will be addressed using a logistic regression model with PTSD diagnosis, history of substance abuse, and site as covariates. Based on review of the studies reported in the Introduction Section, the Planning Committee felt that a 10% difference between treatments would be of clinical relevance given the severity of the illness. With a sample size of 180 per group, the proposed study will have a power of 81% to detect an absolute difference between groups of 10% in the percentage of those participants who remit (6% sham and 16% rTMS). Thus, a total of 360 patients are required. This goal of 360 patients, larger than any previous study, also provides a measure of protection should some assumptions be wrong.

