3.1.2 Analysis Conventions

This section details general policies to be used for the statistical analyses. Departures from these general policies may be given in the specific detailed sections of this statistical analysis plan. When this situation occurs, the rules set forth in the specific section take precedence over the general policies. The following policies will be applied to all data presentations and analyses.

- All statistical tests will use a significance level of $\alpha = 0.05$. Two-tailed tests will be performed for all analyses that use statistical testing.
- All p-values will be rounded to 3 decimal places. All p-values that round to 0.000 will be presented as '<0.001' and p-values that round to 1.000 will be presented as '>0.999'. Any p-value $\leq \alpha$ will be considered statistically significant.
- Summary statistics will consist of the number and percentage of responses in each category for discrete variables, and the mean, median, standard deviation (SD), minimum, and maximum for continuous variables.
- All mean and median values will be formatted to one more decimal place than the measured value. Standard deviation values will be formatted to two more decimal places than the measured value.
- All percentages will be rounded to one decimal place. The number and percentage of responses will be presented in the form XX (XX.X), where the

- percentage is in the parentheses. The decimal of the percentage may be dropped due to space constraints when creating a table.
- For a continuous variable, if it is normally distributed or approximately normally distributed, Student t test and/or the general linear regression will be performed to test the group difference as proposed in the analysis plan, otherwise, Wilcoxon test and/or a quantile regression will be used as an alternative analysis method; for a categorical variable, Pearson χ^2 test and/or a corresponding generalized linear regression will be performed to test the group difference.
 - All listings will be sorted for presentation in order of treatment group, site number, subject number, and date of procedure or event.
 - All analysis and summary tables will have the population sample size for each treatment group in the column heading.
 - Calculating change from baseline to a visit will be done as follows: change = visit –baseline.

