3.9.2 Prognostic Factor Analysis

Prognostic factors or predictors of treatment efficacy for the primary outcome (HRSD) and major secondary outcome measures (MADRS, BSS, BDI, and VR-36) at each time point of the baseline, end of acute treatment, and end of follow-up, will be explored using demographic information and baseline assessments such as age, baseline severity, type of comorbidity (PTSD, substance abuse, or both), duration of illness, prior treatment resistance, concomitant medication use, and possibly their interaction with the treatment. The analyses will be performed on all ITT, completer, and fully compliant populations. Linear or generalized linear mixed regressions will be used to model moderate effect with the factors described above on the treatment efficacy, depending on whether the outcome measure is continuous or categorical. The modeling approach is the same as described in the corresponding sections of the primary and secondary outcome analyses (Tables 3.9.5a-c).

In the event that a multiple regression does not converge when all covariates are included, the model will be refit by dropping the problematic covariate from the model and perhaps investigating it in a separate single-covariate model.

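### If the primary logistic model does not converge, the SAP drops substance abuse and PTSD before Site, an order that cannot cure the likeliest cause, a site with no remitters

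*SAP*

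**What the plan says.** Section 3.7.1.1 specifies logistic regression on the ITT population with treatment, PTSD diagnosis, history of substance abuse and Site (nine sites). The null hypothesis is rejected if the confidence interval for the treatment odds ratio excludes 1. On non-convergence, "the model will be refit by dropping the covariates from the model one at a time in the following order until convergence is obtained". The order is (a) substance abuse, (b) PTSD, (c) Site, so step (c) leaves treatment alone. Non-convergence is not defined, and no penalised, exact or conditional method is named.

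Section 3.7 extends the rule: convergence difficulties in efficacy analyses with covariates "will be handled using the method described in Section 3.7.1". Section 3.9.2 takes another route for the prognostic models: "the model will be refit by dropping the problematic covariate from the model".

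The design figures are in section 2.6: "With a sample size of 180 per group, the proposed study will have a power of 81"%, at "6% sham and 16% rTMS", and "Thus, a total of 360 patients are required". Drop-outs count as failures, so they stay in the denominator and add no remitters.

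**The concern.** A fallback rule should act on the likely reason for failure. With few events and eight Site parameters, that reason is a site where nobody remits: its coefficient has no finite maximum-likelihood estimate. PTSD and substance abuse each split the whole sample in two, so an empty event cell there is far less likely unless one level is rare. The stated order removes these two sound covariates first, leaves the cause in place, and removes Site last.

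What is at stake is whether the confirmatory odds ratio is adjusted for three pre-specified covariates or for none, with the pattern of outcomes by site deciding.

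**Working it through.** **Inputs.** 180 per group, 6% and 16% remission (SAP 2.6); 1:1 allocation and nine sites (2.3, 3.7.1.1); "Two-tailed tests will be performed for all analyses that use statistical testing" at the 5% level (3.1.2). Site sizes and the prevalences of PTSD and substance abuse are not in the SAP, so those below are assumptions. Site is taken as categorical, although the displayed formula shows a single Site coefficient.

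**The SAP's power figure.** With continuity correction:
- SE0 = √(2 × 0.11 × 0.89 / 180) = 0.0330
- SE1 = √((0.06 × 0.94 + 0.16 × 0.84) / 180) = 0.0326
- Power = Φ((0.10 − 1/180 − 1.96 × 0.0330) / 0.0326) = 82.0%

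This is within about a point of the stated 81%, which is not in dispute. The uncorrected formula gives 86.1%.

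**Events.** 180 × 0.06 + 180 × 0.16 = 10.8 + 28.8 = 39.6 remitters. That is 39.6/9 = 4.4 per site and 39.6/11 = 3.6 per non-intercept parameter (1 treatment + 2 binary + 8 Site).

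**A site with no remitters.** For n patients per arm at a site, P0 = 0.94^n × 0.84^n. Over the sites, P(at least one) = 1 − Π(1 − P0). With 20 + 20 patients at each site:
- P0 = 0.94^20 × 0.84^20 = 0.0089
- 1 − (1 − 0.0089)^9 = 7.7%

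| Site sizes (total 360) | 6% / 16% | 6% / 6% |
|---|---|---|
| nine of 40 | 7.7% | 54.7% |
| 60, 55, 50, 45, 40, 35, 30, 25, 20 (assumed) | 19.5% | 67.7% |
| 70, 60, 50, 40, 40, 30, 30, 20, 20 (assumed) | 24.3% | 72.3% |
| 80, 60, 50, 50, 40, 30, 20, 20, 10 (assumed) | 45.6% | 84.1% |
| 80, 65, 55, 45, 40, 30, 20, 15, 10 (assumed) | 50.2% | 86.5% |

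With equal sites the figure is 22.7% at 6%/11%, and 8.2% if both arms remit at 11%.

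**A binary covariate level with no remitters.** If the rarer level holds a share f of each arm, P = (0.94 × 0.84)^(180f). This is 6 × 10⁻¹⁰ at f = 50%, 2.9 × 10⁻⁶ at 30%, 0.0002 at 20%, 1.4% at 10% and 11.9% at 5%. A binary covariate rivals Site as a cause only if one level is very rare.

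**Applying the drop order.** In 3,000 simulated trials per scenario, with both binary covariates at 50% prevalence and separation counted as non-convergence, every failure came from Site. Every failure ended in the unadjusted model: 8.4% of trials with equal sites and 45.8% with the 80, 60, …, 10 profile, both at 6%/16%.

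**Effect on the treatment estimate.** A site without remitters sends only its own coefficient to infinity; the treatment coefficient stays finite. In three simulated separated datasets the full and unadjusted treatment log-odds ratios were 1.135 and 1.141, 1.041 and 0.997, and 0.220 and 0.248. In all three, a Newton fit reported convergence with a largest coefficient of about 30.

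**The case against.** **The rule may not fire.** The SAP does not say what counts as non-convergence. As the last check shows, software can stop with a huge Site coefficient and report success, in which case nothing is dropped. This stands: the probabilities above are chances of separation, and they become chances of an unadjusted analysis only if separation is treated as non-convergence. It also means that two analysts could reach different primary models from the same data.

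**The large percentages are not the SAP's.** A reader might infer that the primary analysis will probably collapse. The documents do not support that. At the planned rates with equal sites the figure is about 8%. The 20% to 50% range needs an assumed enrolment profile, and the 55% needs the active arm to remit at only 6%.

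**The inference barely moves.** A reader might also infer bias or a distorted error rate. Simulation with non-prognostic covariates, taking separation as triggering the rule, shows neither:
- Power was 86.6% for both the full model and the SAP rule with equal sites, and 87.4% for both with uneven sites.
- Null rejection was 3.8% to 5.2% under the SAP rule, against 4.2% to 5.5% for the full model.
- In separated datasets the two tests agreed in 96% to 99% of trials, with a median log-odds-ratio difference of 0.02 to 0.04.

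With prognostic covariates the rule cost about 2 to 3 points of power in the affected datasets, with size at or slightly below nominal.

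**Reach is narrower than section 3.7 suggests.** The mixed models for HRSD, MADRS, BDI, BSS, VR-36, QIDS-C16 and BHS scores have their own rule, a switch to compound symmetry, and section 3.1.2 gives specific sections precedence over general policies. The cognitive models use covariates that the drop list cannot order.

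**Section 3.9.2 is not a contradiction.** It governs exploratory modelling, where picking the troublesome covariate after seeing the data is tolerable. A confirmatory model has good reason to fix its rule in advance. What remains is that the order fixed here does not address the likely cause.

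**Conclusion.** The point holds as a defect in the fallback rule. At the SAP's own rates a site without remitters is the most plausible reason for the primary model to fail, and the stated order removes two sound covariates without curing it before ending in an unadjusted model. The chance of such a site is about 8% with nine equal sites at 6%/16%, and higher if sites are uneven or the rTMS rate is lower.

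The consequence is modest: a pre-specified adjustment lost without need, at a point decided by the outcome data, and a small loss of power if the covariates are prognostic. The conclusion assumes that Site is categorical, that separation counts as non-convergence, and that neither binary covariate has a very rare level. It is worth correcting before analysis because correction is cheap; it does not threaten the validity of the primary test.

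**What to change.** In section 3.7.1.1:

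1. Define non-convergence to include complete and quasi-complete separation.
2. Replace the drop list with one named fallback: the same model, with treatment, PTSD, substance abuse and Site, refitted by Firth penalised likelihood (PROC LOGISTIC with the FIRTH option) and a profile-likelihood 95% interval. Keep the decision rule that the interval must exclude 1.
3. Name only this method. Offering a choice, for example between Firth and site-stratified conditional logistic regression, would add discretion that the current rule does not allow.

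Apply the same fallback to the response model (3.7.1.2.2) and to the visit-by-visit remission logistic models (3.7.1.2.3 and 3.7.1.2.4) where they carry the same three covariates. Narrow the cross-reference in section 3.7 accordingly. The continuous-score mixed models keep their compound-symmetry rule. The binary generalized linear mixed models in 3.7.1.2.3 and 3.7.1.2.4 state no rule of their own, so one sentence should say what applies there.

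The cost is one paragraph and one SAS option, with no new data and no change when the planned model fits. The downside is that, in the fallback case, the estimate and interval differ slightly from the PROC GENMOD maximum-likelihood ones, which the report should say.
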